4.9 Definition of DLT

A DLT will be defined as any of the following adverse events that cannot be considered primarily related to the underlying malignancy, a comorbid condition, or a concomitant medication, occurring between day 1 and day 28 of cycle 1 (with the exception of hematologic toxicity which may be assessed up to day 42 of cycle 1)

Any \geq grade 3 non-hematologic toxicity with the following exceptions:

- Grade 3 alopecia
- Grade 3 nausea, vomiting, diarrhea with electrolyte abnormalities lasting less than 48 hours that are not clinically significant and that does not require total parenteral nutrition (TPN), tube-feeding, or hospitalization
- Grade 3 or 4 liver abnormalities (AST, ALT, or alkaline phosphatase) that resolve to < grade 2 within 5 days
- Grade 3 hyperbilrubinemia that resolves to < grade 2 within 5 days
- Grade 3 indirect hyperbilirubinemia
- Infection, unless the infection resulted from unexpectedly complicated by the degree or duration of myelosuppression in the absence of persistent leukemia.

Patients who receive at least a full course of therapy will be considered to be evaluable for toxicity/DLT and will not be replaced unless the PI determines that further additional patients at that dose level are required for safety purposes.

For patients who do not receive venetoclax and/or trametinib on day 1 of cycle 1 due to logistical and/or financial reasons, the DLT period will be extended to 28 days from the first dose of venetoclax and/or trametinib (whichever starts later). For evaluation of neutropenia-related DLT, the DLT period will be 42 days from the first dose of venetoclax and/or trametinib (which ever starts later).

Hematologic toxicity will be defined as failure to recover ANC > $500/\mu$ L or platelet count > $25,000/\mu$ L by day 42. This will be considered DLT. However, for patients with $\geq 5\%$ blasts, myelodysplastic changes, or evidence of disease by flow cytometry/cytogenetics, failure to recover neutrophil or platelet count will not be considered a DLT as this could be the result of persistent disease.

5. CONCOMITANT MEDICATIONS

- Concomitant medications will be documented in the subject's electronic medical record.
- G-CSF is allowed if needed to hasten count recovery at the discretion of the treating physician
- Use of hydroxyurea during the study may be permitted as clinically indicated, on a case-by-case basis and after discussion with the PI
- Intrathecal chemotherapy for prophylaxis or treatment of known or suspected CNS disease may be permitted as clinically indicated, on a case-by-case basis and after discussion with the PI
- Patients may be concurrently enrolling in supportive care clinical trials with exclusion medications that listed below. Other investigational agents that are used for treatment of other cancers will not be allowed.
- Strong CYP3A or p-glycoprotein inducers are not permitted while on study. These agents include but at not limited to: carbamazepine, phenytoin, rifampin and St. John's wart.
- Moderate CYP3A inducers and moderate or strong CYP3A inhibitors are discouraged while on study. If a patient requires use of moderate CYP3A inducers, use with caution. In many instances, such as antifungal prophylaxis with "azole" therapy in neutropenic patients, CYP3A inhibitors are required in AML patients. Venetoclax should be administered at 50% dose reduction in the setting of moderate CYP3A inhibitors (i.e. isavuconazole, ciprofloxacin, diltiazem) and 75% dose reduction with strong CYP3A inhibitors (e.g. voriconazole), with the exception of posaconazole in which an ~83% dose reduction should be used (i.e. 70mg with posaconazole). The venetoclax dose reduction should continue for the duration of co-administration. In the event the co-administered CYP3A inhibitor is discontinued, the assigned venetoclax ramp-up, these agents must be held; however, they may be started or resumed 24-72 hours after the highest planned dose of venetoclax is given, along with the appropriate dose reduction of venetoclax as above. No dose reductions will be performed for azacitidine or trametinib based on concomitant medications.

Drugs involving these enzymes and transporters can be found in the following webpage: http://medicine.iupui.edu/clinpharm/ddis/main-table/

6. STUDY PROCEDURES

6.1. Pre-Treatment Evaluation

- 1. History and physical examination, including vital signs, height, weight, and performance status
- CBC with differential, electrolytes (potassium, calcium, magnesium, bicarbonate, phosphorus), LDH, uric acid, creatinine, liver function tests (AST and/or ALT and total bilirubin). Differential does not need to be performed if white blood cell count is <0.4 K/µL.
- 3. Bone marrow aspirate, cytogenetics, 81-gene mutation panel (or similar mutation screen) must have be sent within 4 weeks of enrollment.
- 4. Peripheral blood and bone marrow samples for correlative studies

- 5. Pregnancy test in female patients of appropriate age and menopausal state within 1 week of first dose
- 6. Echocardiogram or MUGA scan to assess cardiac function within 4 weeks of first dose

All pretreatment evaluation must be performed within 2 weeks of first dose of the study drug, unless otherwise specified as above.

6.2 Evaluation During Study

- 1. History and physical examination, including vital signs and weight prior to each cycle
- 2. Evaluation for toxicity assessment prior to each cycle
- 3. Assessment of concomitant medications prior to each cycle
- 4. In addition to TLS monitoring during the venetoclax ramp-up period (section 4.8), CBC with differential, electrolytes (potassium, calcium, magnesium, bicarbonate, phosphorus), LDH, uric acid, creatinine, liver function tests (AST and/or ALT and total bilirubin) at least 1-2 times per week during cycle 1, then prior to each subsequent cycle. *Differential does not need to be performed if white blood cell count is <0.4 K/μL.*
- 5. Echocardiogram or MUGA scan to assess cardiac function every 2-3 months (for patients still on trametinib)
- Bone marrow aspiration (including flow cytometry for MRD, and cytogenetics [for patients in whom last bone marrow had abnormal cytogenetics]) to be performed at a minimum on:
 - a. Cycle 1 day 21 (±7 days) For patients in marrow remission on the Cycle 1 day 21 bone marrow (i.e. bone marrow blasts <5% or insufficient sample due to hypoplastic or aplastic marrow), venetoclax may be held at the discretion of the treating physician after discussion with the PI in order to allow for peripheral blood count recovery.

 - b. Cycle 1 day 28 (±7 days) will be performed at least 7 days after C1D21 (± 7 days) if marrow remission is not achieved.
 - c. Cycle 2 day 28 (±7 days) only required for patients who did not achieve CR/CRi at end of cycle 1
 - d. Cycle 4 day 28 (±7 days)

During bone marrows at end of cycles 1, 2, and 4 and at the time of relapse, additional aspirate will be collected for correlative studies, including single-cell sequencing. After the end of cycle 4 bone marrow, additional bone marrow assessments should be performed every 2-4 cycles or as clinically indicated.

	Pre	Cycle 1	Cycle 2	Cycle 3	Cycles 4+	End of Treatment	Follow- Up
Informed consent	Х						
History + physical	Х						
Vital signs	Х	Х	Х	Х	Every cycle		
Performance Status	Х						
Concomitant medication and AE assessment	Х	Х	Х	Х	Every cycle		
Toxicity assessment		Х	Х	Х	Every cycle	Х	Х
CBC with diff	Х	Х	Х	Х	Every cycle		
Electrolytes (potassium, calcium, magnesium, bicarbonate phosphorus), LDH, uric acid, creatinine, liver function tests (AST or ALT, total bilirubin)	X	X	X	X	Every cycle		
Bone marrow aspirate	Х	Х	X ¹	İ	X ²		

Pregnancy test (If indicated)	Х			
Echocardiogram or MUGA ³	Х			
Peripheral blood for	Х			
correlative studies				

¹Only required for patients who did not achieve CR/CRi at end of cycle 1

² Every 2-4 cycles or as clinically indicated

³ Repeat every 2-3 months while on therapy (for patients still on trametinib)

Failure to obtain samples for correlative work (e.g. single-cell sequencing) during either the pre-treatment evaluation or during study will not result in a protocol deviation.

6.3 End of treatment visit

At the time of withdrawal, the following study procedures visit should be completed: Evaluation for toxicity assessment 1.

6.4 Follow-up

Thirty days after last dose of the study drugs toxicity assessment will be recorded. This may be done over the phone with a member of the study staff.

6.5 Long-Term Follow-up

After discontinuing study treatment (unless discontinuing due to withdrawal of consent) patients will be followed for disease progression, relapse, and survival. Patients will be followed for survival every 6 months (±3 months) until death via brief phone call, even after being taken off treatment. For patients registered on our long-term follow-up umbrella protocol DR09-0223, survival follow-up may be conducted under that protocol.

7. EFFICACY AND SAFETY ASSESSMENTS

7.1. CRITERIA FOR RESPONSE

Response assessment will be conducted by the PI using standard criteria ¹⁵ and recorded in the patient's electronic medical record.

- 1. Response Criteria for AML:
 - a. Complete Remission (CR): Normalization of the peripheral blood and bone marrow with 5% or less blasts in normocellular or hypercellular marrow with a granulocyte count of 1 x $10^{9}/L$ or above, and platelet count of 100 x $10^{9}/L$. Complete resolution of all sites of extramedullary disease is required for CR.
 - b. CR without minimal residual disease (CR_{MRD-}) = CR with negativity by multicolor flow cytometry.
 - c. Complete remission without recovery of counts (CRi): Peripheral blood and marrow results as for CR, but with incomplete recover of counts (platelets < 100 x $10^{9}/L$ or neutrophils < 1 x $10^{9}/L$).
 - d. Morphologic leukemia-free state (MLFS) = Bone marrow blasts <5%; absence of blasts with Auer rods: absence of extramedullary disease: no hematologic recovery required. At least 200 cells should be enumerated or cellularity of the bone marrow should be at least 10%.

- e. Partial remission (PR) = All hematologic criteria of CR; decrease of bone marrow blast percentage to 5% 25%, and decrease of pretreatment bone marrow blast percentage by ≥50%.
- f. Stable disease (SD) = Absence of CRMRD-, CR, CRi, PR, MLFS; and criteria for PD not met.
- g. Progressive disease (PD) = Evidence for an increase in bone marrow blast percentage and/or increase of absolute blast count in the blood:
 - i. >50% increase in marrow blasts (must be confirmed by repeat marrow examination ≥4 weeks later) over baseline (a minimum 15% point increase is required in cases with <30% blasts at baseline; or persistent marrow blast percentage of >70% over ≥3 months; without at least a 100% improvement in ANC to an absolute level of >0.5 x 10⁹/L [500/µL], and/or platelet count to >50 x 10⁹/L [50,000/µL] non-transfused); or
 - ii. >50% increase in peripheral blasts to >25 x 10⁹/L (25,000/μL) in the absence of differentiation syndrome; or
 - iii. New extramedullary disease.
- h. Hematologic relapse (after CRMRD-, CR or CRi) = Bone marrow blasts ≥5% or appearance of blasts in the blood, or development of extramedullary disease.
- i. Molecular relapse (after CR_{MRD-}) = Recurrence of MRD by flow cytometry.
- j. The following types of response or treatment failure will be recorded in medical record CR (CR, CR-MRD, or CRi) or what type of treatment failure (SD, PD, hematologic relapse or molecular relapse) they had.
 - i. Complete Remission (CR, CR-MRD, or CRi)
 - ii. Treatment Failure (stable disease, progression or relapse)
 - iii. Inevaluable
 - iv. Not Applicable (N/A)
- 2. For patients with MDS or CMML, the response criteria from the International Working Group as summarized in Cheson BD et al. *Blood* 2006;108(2):419-25 will be used.

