4. TREATMENT OF SUBJECTS

- **4.1.** Variations in doses of the study agents or supportive care medications or dose schedules other than those suggested below are allowed if deemed to be in the best interest of patients. Such changes should be discussed with the PI before they are instituted.
- **4.2.** **Treatment Overview** This will be a phase II, single-arm, open-label study conducted solely at MD Anderson Cancer Center. There will be an initial safety lead-in of 6 patients with relapsed/refractory AML. Patients with newly diagnosed AML will not be enrolled until safety of the combination is confirmed during this safety lead-in.

Cohort A will enroll patients with newly diagnosed AML and Cohort B will enroll patients with relapsed/refractory AML or higher-risk MDS or CMML.

The regimen consists of up to 24 cycles of the combination of azacitidine, venetoclax, and trametinib. Each cycle is anticipated to be 28 days in length, although cycle delays may be made due to delayed count recovery, intercurrent illness, etc.

4.3 Cycle 1 (Induction) – Patients will receive the following agents:

- Azacitidine 75 mg/m2 IV or SC (according to patient preference) on days 1-7 of each cycle
- Venetoclax 100mg on day 1, 200mg on day 2, 400mg on days 3-28
- Trametinib 2mg orally daily

Bone marrow will be performed on cycle 1 day 21 (\pm 7 days). For patients in marrow remission (i.e. bone marrow blasts <5% or insufficient sample due to hypoplastic or aplastic marrow), venetoclax may be held at the discretion of the treating physician after discussion with the PI in order to allow for peripheral blood count recovery.

4.4 Cycles 2-24 (Consolidation) – Patients will receive the following agents:

- Azacitidine 75 mg/m2 IV or SC (according to patient preference) on days 1-7 of each cycle
- Venetoclax 400 mg orally daily on days 1-21
- Trametinib 2mg orally daily

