7.3. CRITERIA TO STOP TREATMENT

- 1. Failure to achieve CR/CRi/MLFS after 6 cycles of treatment, unless the patient is deemed to be deriving clinical benefit (e.g. blast reduction not meeting criteria for CR/CRi/MLFS) as assessed by the treating physician and PI
- 2. Unacceptable toxicity judged to be related to therapy by the investigator, as defined by the NCI Common Toxicity Criteria (irreversible or prolonged (> 42 days) grade 4 hematological toxicity or grade 4 non-hematological toxicity thought to be related to azacitidine, trametinib or venetoclax), unless it has been judged by the treating physician and PI that the patient is achieving clinical benefit.
- 3. Pattern of non-compliance by the patient with protocol requirements or patient's request to be removed from the study.
- 4. Relapse, defined as >5% bone marrow blasts not attributed to hematopoietic recovery, occurring after initial response to therapy
- 5. At the discretion of the treating physician and/or PI

Patients coming off treatment due to the above issues will continue to be followed for survival outcomes.

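### In AML patients the marrow blast limits in Section 7.1 overlap at exactly 5% (CR with PR, and CR/CRi with later relapse), and Section 7.3 defines relapse differently

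*Combined protocol and SAP*

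**What the plan says.** All references are to the combined protocol and SAP.

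- **CR** (7.1, item 1a): "bone marrow with 5% or less blasts in normocellular or hypercellular marrow", with recovered counts.
- **CRi** (7.1, item 1c): "Peripheral blood and marrow results as for CR, but with incomplete recover of counts". The CR blast limit therefore carries over.
- **MLFS** (7.1, item 1d): "Bone marrow blasts <5%; absence of blasts with Auer rods", with no count recovery needed.
- **PR** (7.1, item 1e): "All hematologic criteria of CR", blasts between 5% and 25%, and a fall of at least 50% from pretreatment. The separator between 5% and 25% is lost in the extracted text; it is read here as a range that includes 5%.
- **Hematologic relapse** (7.1, item 1h), which applies only after CR without MRD, CR or CRi: "Bone marrow blasts ≥5% or appearance of blasts in the blood, or development of extramedullary disease".
- **Relapse as a reason to stop treatment** (7.3, item 4), also only after an initial response: "Relapse, defined as >5% bone marrow blasts not attributed to hematopoietic recovery".

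Section 7.4 starts RFS at documented CR/CRi and ends it at relapse or death. It lists relapse among the EFS events. It does not say which definition of relapse applies. The Cohort B primary endpoint (Section 10, Analysis Plan) counts CR, CRi and MLFS within 6 cycles; PR is not counted. MDS and CMML patients are assessed by separate International Working Group criteria (7.1, item 2).

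**The concern.** Response and relapse categories should not share a value unless the plan says which one takes precedence. Here 5% lies inside CR/CRi, inside PR and inside the 7.1 relapse definition. It lies outside MLFS, which is the less demanding category on counts.

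Two things are at stake. The first is the scoring of a first response in Cohort B, where the PI assesses response in an open-label, single-site study and the plan gives no rule for a marrow that fits both CR and PR. The second is the relapse event in RFS and EFS. A patient whose CR or CRi was documented at 5%, and whose next marrow is again 5%, has relapsed by one section and not by the other.

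The second problem also goes beyond the single value of 5%. Section 7.3 sets aside blasts attributed to hematopoietic recovery and Section 7.1 item 1h does not, while Section 5 allows G-CSF. Any marrow of 5% or more whose blasts are attributed to recovery is thus a relapse in 7.1 and not in 7.3.

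**Working it through.** **1. Is 5% inside each limit?**

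| Rule | Limit | 5% inside? | Other conditions |
|---|---|---|---|
| CR, 7.1 item 1a | ≤5% | yes | counts recovered |
| CRi, 7.1 item 1c | ≤5% | yes | counts not recovered |
| MLFS, 7.1 item 1d | <5% | no | none on counts |
| PR, 7.1 item 1e | 5% to 25% | yes | counts recovered; fall ≥50% |
| Relapse, 7.1 item 1h | ≥5% | yes | prior CR or CRi |
| Relapse, 7.3 item 4 | >5% | no | prior response; recovery blasts excluded |

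For a 5% marrow, the PR fall of at least 50% requires (baseline − 5)/baseline ≥ 0.5, so baseline blasts ≥10%.

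**2. What a 5% marrow is called in an AML patient**

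| Case | Meets | Does not meet |
|---|---|---|
| (a) First response, counts recovered, baseline ≥10% | CR and PR | relapse (no prior response) |
| (b) First response, counts not recovered | CRi | PR, MLFS, relapse |
| (c) After CR/CRi, counts recovered, baseline ≥10% | CR, PR, 7.1 relapse | 7.3 relapse |
| (d) After CR/CRi, counts not recovered | CRi, 7.1 relapse | PR, 7.3 relapse |

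Case (a) is the response conflict. Cases (c) and (d) are the relapse conflict.

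**3. The plan's own Cohort B figures**

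Inputs from Section 10: prior Beta(0.7, 1.3), n = 20, target 35%, futility stop if Pr(p < 0.35 | data) > 0.95. The posterior is Beta(0.7 + x, 1.3 + n − x).

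- x = 7, n = 20: Beta(7.7, 14.3), 95% credible interval 0.170 to 0.556. The plan states 0.17 to 0.56, so it reproduces.
- The futility limits of Table 3 (never, 0, 0-1 and 0-2 at 4, 8, 12 and 16 patients) and all 20 cells of Table 4 also reproduce. This point does not disturb them.

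**4. What one patient is worth**

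- 1/20 = 5 percentage points. The bar is 0.35 × 20 = 7 responders.
- 7/20 = 35% meets the bar (interval 0.17 to 0.56). 6/20 = 30% does not (interval 0.14 to 0.51).
- Interim looks, Pr(p < 0.35 | data): 0/8 gives 0.991 and 1/8 gives 0.921; 1/12 gives 0.983 and 2/12 gives 0.920; 2/16 gives 0.979 and 3/16 gives 0.924. In each pair the lower count stops the cohort and the higher does not.

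**5. Range for the unknown frequency**

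The documents do not say how often a best marrow is exactly 5%. As an assumption, let such marrows supply 0, 5 or 10 points of a 35% response rate. If they are not counted, the rate becomes 35%, 30% or 25%:

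| Rate counted | P(at least 7 of 20), ignoring early stopping | P(futility stop) |
|---|---|---|
| 35% | 0.58 | 0.07 |
| 30% | 0.39 | 0.14 |
| 25% | 0.21 | 0.25 |

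These show sensitivity to the definition; they do not estimate an error in the plan.

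**The case against.** The strongest reply is that the Cohort B primary endpoint, read literally, is determinate. It counts every patient who achieves CR, CRi or MLFS. A 5% marrow that meets the other CR or CRi conditions is in the numerator, and also meeting PR does not take it out. PR enters no endpoint in Section 7.4 and is not among the outcomes to be recorded under 7.1 item 1j. This stands. A reader might infer that the current text yields two primary results, 7/20 and 6/20; it does not. That difference appears only if the definition is changed or the assessor scores the marrow as PR, which the missing precedence rule leaves possible.

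A reader might also infer that one marrow can be response, PR and relapse at once when response is first scored, or that RFS can start and end on the same sample. The documents do not support either. Relapse in 7.1 requires a prior CR or CRi, so all three labels meet only on a later marrow (case c), in a patient who is already a responder. Nor does PR overlap CRi, since PR needs recovered counts.

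It is also fair to say that any single misclassification moves a 20-patient cohort by 5 points, so that figure does not measure how common this problem is.

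Finally, some limits serve other purposes. The day-21 marrow remission limit in Sections 4.3 and 6.2 ("bone marrow blasts <5% or insufficient sample due to hypoplastic or aplastic marrow") bears on a discretionary venetoclax hold and is not an endpoint. Section 7.3 item 4 is a treatment-stopping rule and may legitimately differ from an endpoint definition. But Section 7.4 names relapse without a source, so the difference still leaves RFS and EFS undefined.

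**Conclusion.** The concern holds in a limited form. In AML patients the 7.1 limits overlap at exactly 5%: CR with PR at first response, and CR/CRi with relapse afterwards. The clearest defect is in the secondary endpoints. An unchanged 5% marrow after CR/CRi is an RFS and EFS event under 7.1 and not under 7.3, the recovery exclusion appears in only one of the two sections, and Section 7.4 does not choose between them. For the Cohort B primary endpoint the defect is the absence of a precedence rule between CR and PR.

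The size is 5 percentage points per affected Cohort B patient, at an unknown frequency. It rests on reading the PR range as including 5%, and it concerns only the AML patients in that cohort. The overlap does not reach Cohort A's primary endpoint (1-year overall survival) or responses in MDS/CMML patients; RFS and EFS in Cohort A are exposed.

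**What to change.** 1. In 7.1 item 1a, change the CR marrow limit from at most 5% to <5%. CRi follows automatically. This agrees with the protocol's own MLFS, PR and 7.1 relapse limits and removes the CR/PR and CR/relapse overlaps.
2. In Section 7.4, name one relapse definition for RFS and EFS, and state whether blasts attributed to hematopoietic recovery are excluded.
3. The investigator must reconcile 7.3 item 4 with 7.1 item 1h. This review takes no position on which stopping threshold is right.

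The first change does not make every category exclusive. A marrow below 5% with low counts can still be both CRi and MLFS. Both count in the primary endpoint, but RFS and the overall response rate in 7.4 use CR/CRi only. On a later marrow, PR and relapse also still share 5% to 25%, which matters little because PR enters no endpoint in 7.4.

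The cost is a short wording amendment, best made before responses are scored, and a check of the other places that rely on CR or CRi (Sections 4.7, 6.2 and 7.3). The downside is that a patient whose best marrow is exactly 5% would no longer count as CR/CRi, so the Cohort B rate may be slightly lower, by 5 points per such patient. The design calculations need no change.

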7.2. EVALUATION OF TOXICITY

1. Toxicities will be graded according to the NCI Common Toxicity Criteria for Adverse Event Reporting Version 5.0. The toxicity of the regimen will be monitored continuously during the course of the study.

